In response to the IRB's decision that therapists in Trials 2 and 3 will be engaged in research activity, participation in Trials 2 and 3 will be limited to therapists within Mayo Clinic (Rochester and Health System) and external organizations that have an IRB and with which we complete a reliance agreement. Recruitment of therapists within Mayo Clinic (Mayo Clinic will be used to refer to Rochester and Health System) will be conducted by the study staff (PI, study coordinator, intervention specialists) directly through emails and phone calls (scripts included in this modification). In addition, study staff will provide the recruitment scripts to division leaders and supervisors to ensure that recruitment and participation in the study is consistent with clinical programming. Finally, the study staff will provide recruitment materials to members of the Convergence Child Specialty Council to provide interested clinicians with familiar contact to discuss the study. All efforts to recruit clinicians will emphasize the voluntary nature of the study and that declining to participate will have no effect on their employment or care through Mayo Clinic. Our study staff will directly contact external institutions that provide child mental health care to determine if they would be interested in partnering in this project. Only institutions that have at least 5 interested and appropriate therapists will be contracted with. We anticipate entering agreements with up to 4 organizations in order to enroll 30 therapists for Trial II. The Mayo Clinic IRB will serve as the IRB of record for the collaborating institutions. Recruitment of therapists within the partnering institutions will be implemented by a site-PI following the procedures consistent with those used within Mayo Clinic. Trial 3 will involve therapists from the study staff providing treatment.

Therapists that are interested in participating but are not covered by an IRB, will be enrolled in the first trial, i.e., acceptability study.

C.3.b. Phase II: Therapist Trials (18 months). The second phase of this proposal will address Aim 2 of assessing the feasibility, safety, acceptance, and impact of *Anxiety Coach* through three trials.

Note: The current modification covers the initiation of Trial 2 and Trial 3. Trial 1 has been approved and enrollment as begun.

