Trial 3. In Trial 3 (Increasing Access) children with anxiety disorders will be randomized to receive with MC-AC delivered by therapists in the Pediatric Anxiety Disorders Clinic (study staff) or treatment as usual in the community or within Mayo Clinic, just not with their current therapist. Data collection will include questionnaires completed by therapists, patients, and parents before and after treatment, as well as data automatically saved by the application. Following the study all patients will be offered treatment within the Pediatric Anxiety Disorders Clinic. Patients in the community treatment group will also receive the Anxiety Coach application.

C.3.c. Phase III: Revision Stage (4 months). During the final 4 months the feasibility data will be analyzed along with feedback from patients and therapists. This data will be used to revise the protocol for training therapists to use *Anxiety Coach*, prepare a manuscript for publication, and apply for R01 funding to conduct a fully powered randomized controlled trial to evaluate the symptom improvement and cost-efficiency of using *Anxiety Coach* to provide minimal contact care and disseminate evidence-based treatment.

C.4. Participant Availability and Recruitment. The outpatient mental health therapists in Trial 2 will be recruited and will subsequently recruit their own patients into the study. The therapists will be provided an iPod Touch for participating in the study that they can keep. Before recruiting patients, therapists will complete appropriate training in research ethics. Patients will be recruited by the therapists during their initial evaluation. Patients will be screened and consented by study staff. Patients **and therapists** in each condition will be reimbursed for completing study assessments and recordings (\$100 total) and will receive an iPod Touch that they can keep. Partnering institutions in the minimal contact condition can be reimbursed for non-billable time spent on the *Anxiety Coach* portal at a rate of \$146.34 per hour up to 6 hours. The therapists for Trial 1 have largely been recruited under the initially approved IRB protocol. Additional therapists will be recruited as needed.

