C.5.e. Treatment as usual (TAU). The control condition in Trial 3 will consist of having the family participate in the existing clinical services offered by the therapist over the 12-week period. After 12-weeks they will be asked to sign a release of information to have the any outside treatment records sent for review by the study staff. The records will be coded for treatment components. As the post-study evaluations, patients in the TAU condition will receive Anxiety Coach and be offered additional treatment as needed.

C.6. Design Considerations

C.6.a. Justification of Experimental Design. The use of three conditions across two trials allows for an examination of the effects of *Anxiety Coach* and direct therapist contact. Specifically, the **TAU vs. FTF-AC comparison** provides an estimate of the feasibility and palatability of *Anxiety Coach* to therapists, a measure

of the extent to which the application facilitates therapists' use of exposure-based methods, the usefulness of *Anxiety Coach* for disseminating evidence-based CBT methods to community therapists, and its value for facilitating treatment adherence among patients with anxiety disorders. Randomizing therapists/patients to one of two conditions removes the potential for bias to affect recruitment, keeps the evaluators blind to experimental condition, removes concerns with order effects, and allows for the more patients to be treated simultaneously thus decreasing the length of the study. **The MC-AC vs. TAU comparison** provides an estimate of the feasibility as well as the impact on acceptability and outcome of using *Anxiety Coach* with limited direct therapist contact as a method for extending treatment outside of the brick and mortar mental health settings. To increase the real-world generalizability of the study, the study will not pay for therapy, but patients in all conditions will be reimbursed for participation in assessments and will be allowed to keep the iPod Touch.

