C.7.a. Therapist Survey. A survey will be sent to all the mental health providers contracted by MMSI under IRB 14-002608. Therapists that practice in areas designated by the U.S. Department of Health and Human Services as Mental Health Care Health Professional Shortage Areas,⁷⁸ treat children with anxiety disorders, endorse openness to CBT, and report infrequent use of exposure will be recruited into the study.

C.7.b. Therapist Telephone Screening and Consent. Therapist eligibility and interest in participating in the study will be assessed through phone screening completed by the study team. Information regarding licensure status, frequency of treating children with anxiety disorders, and openness to piloting a smartphone-based CBT aide will be confirmed by the therapists' institution. Therapists that meet inclusion/exclusion criteria will be mailed a consent form.

C.7.c. Patient Telephone Screening. For Trials 2 and 3, a multi-gate screening procedure will be used to recruit patients. Interested patients evaluated as part of clinical practice by participating therapists will be an informational letter, instructions, two copies of the consent/assent documents, parent- and child-report forms, and instructions to contact the study team for pre-consent screening. Therapists will also relay patient name and information to study staff via telephone for contact. During the screening call, information regarding the

patient's symptoms, previous treatment and diagnoses, and willingness to be assigned to one of three treatment conditions will be gathered. The number of callers deemed ineligible and reasons for ineligibility will be recorded in the Screening Log. If patient is likely to be eligible, a consent and evaluation videophone visit will be scheduled. This visit should occur within 1 week (+/- 1 week) from the initial therapist visit.

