One potential risk of participating in this project includes discomfort during the data collection (survey, phone screenings, and assessments) related to discussing sensitive topics and the length of the evaluation. However, the length of material completed by therapists are minimal and the patients in the study are seeking treatment and presumably are interested in discussing their symptoms with an expert clinician. It is estimated that the survey will require 20 to 30 minutes to complete, and the patient interview and questionnaire completion will take approximately 2-3 hours for the initial evaluation and 1-2 hours for the post-treatment assessment. Having the family complete questionnaire packets at home where the family can work at their own pace and take breaks will minimize the burden associated with lengthy assessments.

Although difficult to predict with certainty, the degree of risk and benefit may differ among the three conditions. Neither the relative benefit of augmenting face-to-face therapy with *Mayo Clinic Anxiety Coach* nor the relative risk of minimal contact treatment have yet been tested, and so the relative cost-benefit ratios are uncertain. The risk of being randomized to TAU is that the patient may receive a potentially less effective treatment. However, as this treatment is the standard intervention outside the study, participation in the study will not have a detrimental effect on the quality of the patient's treatment. In fact, the study requirement of a minimum of 6 sessions will likely result in a higher level of care. Further, there is no portion of the study during which patients will be asked to receive no treatment. Alternatively, patients in the minimal contact *Anxiety Coach* condition may be at risk of receiving a less effective treatment because of the decreased therapist contact. However, the goal of the study is to examine the feasibility of minimal contact treatment. Thus, patients may receive emergent care or more frequent contact if needed. Such occurrences will be collected as measures of tolerability. Within all conditions if additional care is clinically indicated the therapist (with the assistance of the study staff under the direction of [name]) will assist the family in making arrangements for appropriate care.

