Patients (children and caregivers) will be recruited for participation in the study by the enrolled therapists. During the initial evaluation the therapist will describe the study including its voluntary nature using a prepared script. The therapists will provide families that express interest in participation a study packet and encourage them to contact study staff to schedule screening visit. The study coordinator will conduct a phone screening with the caregiver including questions to assess the presence of an anxiety disorder and obtain other information relevant to inclusion and exclusion criteria (e.g., diagnostic and treatment history). Those who are determined to be ineligible will be offered other treatment options including treatment with the referring therapist, an evaluation at Mayo Clinic outside of the study if appropriate, and resources for finding other providers. Those who appear to be eligible will be scheduled for the videophone Consent and Evaluation visit. During the initial part of this visit, the patient and parents will be given a review of the informed consent document including information about the treatment options within the study, potential risks and benefits of study participation, as well as any alternatives to participating in research. The investigators will try to foster an open exchange of information and will encourage the child and caregivers to ask questions and discuss concerns. It will be the responsibility of [name] to ensure that all participants (therapists, patients, and caregivers) have provided consent/assent and understand their role in the research. Participants will be told that they can discontinue participation at any time, or refuse to answer any study questions, without adverse consequences. If patients and caregivers are interested in participation, a copy of the consent and assent documents will be signed and placed in the postage-paid envelope included with the study packet. To minimize delay in beginning therapeutic treatment, the pre-treatment evaluation will be conducted at this visit. However, patients will not be considered to be enrolled in the study until the signed consent/assent documents have been received and signed by study staff. In the event that data is collected but signed consent/assent documents are not received, data will be excluded from any research-related activities or analyses. Data on screening, eligibility decisions, and enrollment will be tracked.

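### Trial 3's usual-care control is defined in two conflicting ways, the no-detriment assurance fails on one of them, and Time 2 slides or vanishes for controls whose care starts late or never

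*Protocol*

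**What the plan says.** **Assurances about TAU (Protocol 4.1.1.c).** The section first concedes that TAU may be the less effective treatment. It then argues, about the standard of care received, that "as this treatment is the standard intervention outside the study, participation in the study will not have a detrimental effect on the quality", and it adds that "the study requirement of a minimum of 6 sessions will likely result in a higher level of care". Neither statement is limited to one trial.

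**The Trial 3 control.** C.3.b describes it as "treatment as usual in the community or within Mayo Clinic, just not with their current therapist". C.5.e describes it as use of the "existing clinical services offered by the therapist over the 12-week period", after which the family is asked to sign a "release of information to have the any outside treatment records sent for review by the study staff".

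**How children arrive.** For Trials 2 and 3, C.7.c starts from "Interested patients evaluated as part of clinical practice by participating therapists". Section 4.1.2.a adds: "Those who are determined to be ineligible will be offered other treatment options including treatment with the referring therapist".

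**Who treats, and how much.** C.3.a.4 says "Trial 3 will involve therapists from the study staff providing treatment". C.8.d applies weekly contact for 6 to 12 weeks to each intervention in Trials 2 and 3 and names a six-session minimum when discussing TAU. The detailed TAU session format (C.5.b) and the weekly specialist review (C.5.a) are labelled Trial 2.

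**Timing and analysis set.** C.7.g puts Time 2 at 12 weeks, give or take 2, from the first treatment session, and expects treatment to start one to two weeks after baseline. C.7.e places Trial 3 assignment after consent and the baseline evaluation. C.10.c makes intention to treat the principal analysis set.

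**The concern.** Two things are at stake.

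The first is the accuracy of a risk statement about children. The no-detriment argument works only if TAU is what the child would have received anyway. It fits Trial 2, where the recruiting therapist goes on to treat. In Trial 3, on the C.3.b wording, assignment to control can remove the therapist who has just evaluated the child, whereas a child found ineligible may still be treated by that therapist.

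The second is the comparison itself. MC-AC is delivered by study staff who are already in place. Controls may have to find someone, and the protocol assigns nobody to arrange it. Because the outcome visit is tied to the first session, late control care pushes the visit back, and absent control care removes it. Assessment time then differs by arm for a reason produced by the assignment. C.10.b.2 wants these estimates for planning a full trial.

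**Working it through.** The plan states no figure to reproduce. The check sets the sections side by side and then does date arithmetic on C.7.g.

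**1. Who may treat a Trial 3 control?**
- If the current therapist in C.3.b is the referring therapist, C.3.b excludes that person, while C.5.e, on its natural reading, sends the family to that person. C.5.e does not use the word current, so the conflict lies in the natural reading rather than the literal one.
- If the current therapist is a study-staff clinician who evaluated the child, the clause is a safeguard against contamination. C.3.b does not say this, and C.5.e does not identify its therapist.
- On either reading, the control has no single stated definition.

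**2. Does the no-detriment premise hold?** It requires TAU to equal care outside the study. By 4.1.2.a, care outside the study includes the referring therapist. By C.3.b on the first reading, control care does not. The premise fails on that reading.

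**3. Can the six-session minimum be applied?** C.8.d states it for Trials 2 and 3. C.7.f says the specialists or the principal investigator will monitor compliance in all three conditions. But C.3.a.4 names only study staff as Trial 3 therapists, C.5.e gives no minimum, and control records are requested only after 12 weeks. No section says how an outside provider would be instructed or followed during treatment.

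**4. When is Time 2?** Let w be weeks from baseline to first session. By C.7.g, Time 2 = w + 12 ± 2, that is, w + 10 to w + 14.

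| Child | w | Time 2, weeks from baseline |
|---|---|---|
| MC-AC, earliest expected start | 1 | 11 to 15 |
| MC-AC, latest expected start | 2 | 12 to 16 |
| Control, delay assumed | 4 | 14 to 18 |
| Control, delay assumed | 8 | 18 to 22 |
| Control, never starts | none | undefined |

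The expected MC-AC range is therefore 11 to 16 weeks. A control's whole window falls beyond it once w + 10 > 16, that is, w > 6. The control delays are illustrations; the documents give no waiting times.

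**5. How much does one child count?** Aim 2 gives 30 patients in Trial 3. The allocation ratio is not stated; at 1:1 there are 15 controls, and 1/15 = 6.7%.

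**6. What would randomization dating do?** Time 2 becomes 12 ± 2, or 10 to 14 weeks from randomization, in both arms. Taking randomization as the day of evaluation, MC-AC children starting at week 1 to 2 have 12 − 1 = 11 to 12 − 2 = 10 weeks of treatment before the nominal date, instead of 12.

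**The case against.** The case on the other side has real content.

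- **The minimum is stated for Trial 3.** A reader might infer that it has no basis there. C.8.d shows otherwise. What stands is narrower: the means of applying it to an outside provider is missing.
- **The protocol is candid about TAU.** A reader might take 4.1.1.c to promise that TAU cannot be worse. It says just beforehand that TAU may be less effective. What fails is the reason then given for no detriment.
- **Nobody is asked to go untreated.** That sentence in 4.1.1.c is not contradicted. Sections 4.1.1.c, 4.1.2.b and 4.1.5 provide for monitoring and additional care, so a reading that controls are abandoned is not supported.
- **A start is expected.** C.7.g foresees treatment within one to two weeks, so controls who begin on time do have a Time 2 date. C.7.e also seeks early-withdrawal evaluations, which helps with discontinuation but sets no date for a child who never began. Only delayed or absent care lacks a rule.
- **Usual care may come from within Mayo Clinic.** This weakens any claim that controls would generally struggle to find a provider.
- **Slow access may belong to the contrast.** Trial 3 concerns access, so ordinary delay is arguably part of usual care. That does not cover delay caused by excluding the current therapist, nor does it justify assessing the arms at different times.
- **The analyses are exploratory.** C.10.a, C.10.b.2 and the SAP make them mainly descriptive, which limits the inferential damage.

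**Conclusion.** The point holds in limited form. C.3.b and C.5.e conflict on who delivers the Trial 3 control. On the C.3.b wording, the no-detriment reasoning in 4.1.1.c does not carry to Trial 3. The six-session minimum reaches Trial 3 controls on paper only. The C.7.g rule delays Time 2 by one week for every week that control care is delayed, and gives no date when care never starts.

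The size rests on assumed delays and 1:1 allocation: no overlap with the MC-AC range once a control starts after week 6, and 6.7% of the control arm for each child without a date. The harm to the child rests on reading the current therapist as the referring therapist, which the text permits but does not settle.

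Two further inferences are not supported. A reader might add lost sessions to a late Time 2. Sessions are lost only if C.5.e's 12 weeks run from a fixed point such as assignment; under C.7.g a late starter still has about 12 weeks before Time 2. The protocol does not say which clock governs, and one child cannot incur both. A reader might also put a number on the bias in the Trial 3 difference. The documents give neither the share of controls who go untreated nor the effect of usual care, so no number can be defended. Because the study is a pilot with exploratory comparisons, this should be corrected but does not invalidate the design.

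**What to change.** 1. **Time 2.** In Trial 3, set it at 12 (± 2) weeks from randomization in both arms (C.7.g), and start C.5.e's 12-week period at the same point. Cost: MC-AC children have 1 to 2 weeks less treatment before Time 2, so a child using the full 12 weeks allowed by C.5.d would finish after the nominal date.
2. **Control provider.** Define it once, in the same words in C.3.b and C.5.e, and state whether the referring therapist is allowed. Allowing that therapist may strengthen control care and narrow the difference; excluding that therapist keeps the risk of delay and must then be disclosed as a risk.
3. **Assurances.** In 4.1.1.c, limit the no-detriment and six-session statements to Trial 2, or state how each applies to Trial 3 controls. Align C.8.d.
4. **Reporting.** For Trial 3 controls, report whether any session occurred, the first-session date and the number of sessions, beside the symptom results. The records in C.5.e supply these where a release is signed; show an unsigned release separately from no care received.

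Items 1 to 3 are an amendment to five sections with no extra visits. If enrolment has ended, item 4 is still feasible and the others carry into the full trial. I would not require control appointments to be booked before randomization, because that would make usual care less naturalistic, a quality C.6.b values.

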4.1.2 Adequacy of Protection Against Risk

4.1.2.a. Recruitment and Informed Consent: Recruitment will begin with a survey sent to all mental health providers contracted by MMSI conducted under IRB 14-002608. The survey will include consent language approved by the Institutional Review Board and require the participant to actively indicate understanding and willingness to consent. Recipients will be able to decline participation and indicate that they do not wish to be contacted again (i.e., the follow-up to nonresponders). The SRC will provide a de-identified data set to the study team who will identify all eligible participants. The SRC will provide the name and contact information for a randomly selected recruitment pool of 80 therapists (or more if needed), but not the associated code numbers. During the screening phone call placed by the project director, the study will be described (including inclusion criteria) and the therapists will be invited to participate. Those interested will have the consent form reviewed and be mailed two copies (one to return, one for their records). Only after one copy of the written consent form has been received will the study staff verify that the therapist is licensed and does not have a history of disciplinary action. Therapists will then complete appropriate research ethics and HIPAA training.

Patients (children and caregivers) will be recruited for participation in the study by the enrolled therapists. During the initial evaluation the therapist will describe the study including its voluntary nature using a prepared script. The therapists will provide families that express interest in participation a study packet and encourage them to contact study staff to schedule screening visit. The study coordinator will conduct a phone screening with the caregiver including questions to assess the presence of an anxiety disorder and obtain other information relevant to inclusion and exclusion criteria (e.g., diagnostic and treatment history). Those who are determined to be ineligible will be offered other treatment options including treatment with the referring therapist, an evaluation at Mayo Clinic outside of the study if appropriate, and resources for finding other providers. Those who appear to be eligible will be scheduled for the videophone Consent and Evaluation visit. During the initial part of this visit, the patient and parents will be given a review of the informed consent document including information about the treatment options within the study, potential risks and benefits of study participation, as well as any alternatives to participating in research. The investigators will try to foster an open exchange of information and will encourage the child and caregivers to ask questions and discuss concerns. It will be the responsibility of [name] to ensure that all participants (therapists, patients, and caregivers) have provided consent/assent and understand their role in the research. Participants will be told that they can discontinue participation at any time, or refuse to answer any study questions, without adverse consequences. If patients and caregivers are interested in participation, a copy of the consent and assent documents will be signed and placed in the postage-paid envelope included with the study packet. To minimize delay in beginning therapeutic treatment, the pre-treatment evaluation will be conducted at this visit. However, patients will not be considered to be enrolled in the study until the signed consent/assent documents have been received and signed by study staff. In the event that data is collected but signed consent/assent documents are not received, data will be excluded from any research-related activities or analyses. Data on screening, eligibility decisions, and enrollment will be tracked.

4.1.2.b. Protections Against Risk:

At the time this application was submitted the Research Committees within the Department of Psychiatry and Psychology and the Department of Pediatrics with Mayo Clinic approved all study procedures including the language in the consent and assent forms to ensure that it is simple and understandable. Prior to the onset of the study, the Mayo Clinic Institutional Review Board will also approve these materials. The research team will carefully protect the confidentiality of all participant research information. Investigators are required to undergo and periodically renew training in research ethics and HIPAA. Given their role in recruiting patients, participating therapists will complete similar training for that role. All paper-generated data, computer-generated data, and session recordings will be labeled with code number unrelated to the patients' identifying information. All paper-generated data will be stored in locked files in the office of [name] or the SRC. All computer-generated data and session recordings will be maintained in password-limited, secure network drive files. Participant names (or other identifying information) will not be kept on the study measures. Instead code numbers will be used and the key linking code numbers with participant identifiers will be kept in locked files separately from the data. Only [name] and the study coordinator (or the SRC for survey data) will have access to the code key. To protect the confidentiality of data collected through the Anxiety Coach application no-identifiable information will be requested. Specifically, rather than requesting full names and birthdates, the system will generate identifiers (e.g. Patient #1) rather than names and allow entry of ages but not birthdates.

The in system messaging capabilities have reminders not to include identifiable information. Patients will be required to agree to the Anxiety Coach Terms of Use that explains what data Mayo Clinic collects and how that data is used. The Terms of Use will inform patients that they have the ability to decline to have their data used for research purposes.

To decrease the likelihood that therapists or families feel coerced to remain in the study or feel it was not worth their investment of time and effort the staff will approach informed consent as a continuous process by: setting clear initial expectations about the research study, routinely assessing participant (patient and therapist) comfort with the study, reviewing the study components that have been completed and that are upcoming at each evaluation time point, supporting non-billable therapist time to manage patients electronically, reimbursing participant families for their time to complete study assessments, and allowing participants (patient and therapist) to keep an iPod Touch. To decrease the likelihood that youth will feel coerced by their parent to participate, the IE who completes the enrollment assessment will directly ask the child if s/he is interested in participating. If the IE has concerns about that the child is feeling coerced he will ask to speak to both the child and the parent individually to gather further information, and then discuss his/he concerns with the PI. If patients deteriorate or develop clinical crises the investigators may recommend adjunctive treatment or study termination. Prematurely terminated participants may continue with study treatment and provide assessment data. All participants randomized to treatment conditions will be included in data analyses and the circumstances surrounding missing data will be recorded.

Thorough screening and assessment will aim to rule out psychiatric conditions in children and caregivers that may prevent families from participating in the study. Once in the study families will be followed closely by a therapist and an intervention specialist with considerable experience providing treatment for childhood anxiety disorders under the supervisor of [name]. [name], the treating therapist, an intervention specialist or a covering clinician through the Mayo Clinic Division of Child Psychiatry and Psychology will be available for research subjects 24 hours a day, 7 days a week. Side effects and adverse events will be monitored closely throughout the study. Specifically, the therapists (or evaluator) will conduct a general inquiry at each contact regarding symptomatology, adverse events, self-harm, or any health complaints. If at any point during the study participants develop elevated risk for harm to self or others, or experience increased symptoms, appropriate treatment will be instituted. Reported complaints will be coded on a standardized form as Mild (minor complaint causing no interference and not requiring intervention), Moderate (more than minimal problem, source of some interference and may require intervention), Severe (significant complaint, definite interference requiring intervention), or Serious (life threatening, a potential for long-term disability, and/or requiring hospitalization). Based on the nature of the complaint the independent evaluator will determine whether it is related to the study, and [name] will take appropriate action (e.g., monitoring, adjunctive intervention, removal from study). Any cases of suspected abuse will be reported consistent with the roles of mandated reporters by the therapist and study staff in conjunction with [name]. Any instances of suspected malpractice by study therapists will be addressed consistent with institutional guidelines, the ethics code of the American Psychological Association, and the credentialing body of the therapist in question.

Protections related to subjects with depression or suicidal ideation are as follows: Patients who endorse severe depression or suicidal ideation during the screening phone call or the initial evaluation will not be enrolled in the study. Patients who endorse mild to moderate depression that is secondary to a primary anxiety disorder during the screening, initial assessment, or post-treatment assessment will be allowed to participate in the study. In all cases of severe or moderate depression, the project director will communicate the results of the patient's depression evaluation to the treating therapist. If during any contact the patient is determined to have active suicidal ideation, appropriate steps will be taken by the project director, [name], and/or the treating therapist to ensure the patient's safety, i.e. emergent evaluation or hospitalization. The PI ([name]) is a board-certified child psychologist with extensive experience treating youth with anxiety disorders, including comorbid suicidality. [name] will follow standard policies and procedures developed by the Mayo Clinic Child and Adolescent Division in the Department of Psychiatry and Psychology, e.g., comprehensive assessment of depressive symptomatology, assessment of suicidal ideation (inclusive of intent, means, plan), immediate notification to the subject's legal guardian, and referral to the Mayo Clinic Child and Adolescent Inpatient Psychiatry unit (in cases of immediate lethality). Implementation of strategies to

mitigate suicidal behavior will be tailored to the specific presenting case. If necessary, additional services, or inpatient treatment will be made available but are not provided by the study.

To address clinically-related crises that may occur during a clinical trial the Adjunct Services and Attrition Prevention procedures and guidelines will be followed, based on an adaptation of the MTA's procedural manual (ASAP)⁹⁴ similar to other NIMH clinical trials (e.g., MTA, POTS). Under ASAP guidelines situations that require interventions will be addressed in a manner that responds appropriately to the emergent clinical needs of the participant families, while, to the extent possible, maintaining the integrity of randomization (i.e., preventing attrition), and limiting contamination of study treatments. This approach is adopted to maintain subjects in the study and intent-to-treat analyses.

In cases where children are receiving anxiety-related medications prior to the period of study eligibility, or where initiation (or discontinuation) of a medication during the study period seems clinically necessary, this care will be managed by prescribing physician. Although we expect that medication changes will be minimal or absent, if such occur, we will analyze outcomes from patients with and without medication changes occurring during the course of the study to determine if changes in outcomes are attributable to medication changes.

